12.4 Safety Data

Safety analysis will be done using the safety set presented by dose and overall.

Extent of exposure

Duration between IMP administration and end of study, volume theoretically administered, volume actually administered, actual rate of administration, theoretical rate of administration will be tabulated.

 CONFIDENTIAL	Protocol No. GDX-44-008 Version No.4.0 including amendments 1 and 2 12 December 2017	Page 52 / 64
---	--	--------------

Frequency tabulation of theoretical volume actually administered and theoretical rate of administration actually performed will be also displayed.

Adverse events

All analyses of AEs will be based on the number of subjects with AEs. Adverse events occurring after D+1 that the investigators considers as related to P03277 /study procedures will be included in this analysis.

Adverse events will be coded with the most recent version of MedDRA at the time of the database lock.

The time period for the assessment of AEs will be divided into 3 mutually exclusive and exhaustive periods: before administration of P03277, after administration of P03277 until day +1 FU and after safety follow-up until biopsy if it is done.

Events will be classified as treatment-emergent (TEAE) if they started or increased after P03277 administration. This will also include events with missing intensity.

Partial start dates/times will be queried. If information is not available to reliably allocate to a session and period, the allocation will be agreed at the data review meeting before database lock. If there is any doubt about treatment emergence, AEs will be classified as treatment emergent.

In all summaries, recurring AEs (AEs classified with the same preferred term) for a given subject in a given period will be counted as a single AE. If severity is summarized, this will be the maximum severity.

Overall overview

The number (%) of subjects having at least one Treatment Emergent AE (TEAE) as follows will be summarized for:

At least one TEAE

At least one adverse reaction (relationship to study treatment classified as 'Related')

At least one TEAE with action taken with study treatment

At least one TEAE with classifications of outcome

The table will show the same information for serious AE, defined as AEs with serious classified as 'yes' or missing.

The table will be repeated for all AEs

Distribution of AEs and SAEs

A table will be presented showing the total numbers of AEs and SAEs and the distribution of AEs (number [%] of subjects with 0, 1, 2 etc... AEs) . The table will also show the same information for SAEs defined as TEAEs with serious classified as 'yes' or missing, unless the number of SAEs make this uninformative.

Summaries by System Organ Classes (SOC) and Preferred Term (PT)

The table of summaries of at least one TEAE will be repeated by SOC only (without the breakdown by PT).

Concomitant medication after P03277 administration

Concomitant medications will be coded using the WHO Drug dictionary and be presented displaying number and frequency by ATC System Main Group and Therapeutic Subgroup.

Guerbet  CONFIDENTIAL	Protocol No. GDX-44-008 Version No.4.0 including amendments 1 and 2 12 December 2017	Page 53 / 64
--	--	--------------

Injection site tolerance

Number of subjects experiencing burning, pain, eruption, extravasation and inflammation at site injection will be tabulated. Pain at injection site will be measured using the Visual Assessment Scale (VAS) and VAS measurements for these subjects will be tabulated.

Laboratory data

The statistical analysis will present results in standard international units and United States units. Original units will be only listed. Laboratory data will be analyzed quantitatively and qualitatively. Qualitative analyses will be done via comparison of laboratory data to their reference ranges and according to their clinical significance. Quantitative analyses will be done by tabulating raw data and change from baseline. They will be displayed qualitatively as well as by means of shift tables.

Vital signs

Vital signs will be analyzed quantitatively and qualitatively. Qualitative analyses will be done via comparison of vital signs data to their normal ranges (see section 7.2.2) and according to their clinical significant changes. Quantitative analyses will be done by tabulating raw data and change from baseline.

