7.2.2 Safety assessment

The safety assessments will be based on the following: Adverse Events (AEs), injection site tolerance, clinical laboratory parameters (blood), vital signs. A central laboratory will be used to analyze and report blood chemistry/hematology. eGFR would also have been evaluated locally only for screening. eGFR evaluated centrally will be used for safety evaluation.

- **Adverse events**

Adverse Event monitoring will be recorded until Day+1. After, AEs that the investigator considers related to P03277 and/or study procedures will be recorded at optional V4.

- **Injection-site tolerance**

For all subjects, injection-site tolerance (burning, pain, eruption, extravasation, inflammation, or other) will be assessed over 1 day following each contrast agent injection (during the injection up to 30 ± 5 mn, and the day after injection) and over a longer period if the investigator becomes aware of any related AE. In case of injection-site pain, the subject will be asked to specify the level of pain using a visual analogic scale (VAS, [REDACTED]) from 0 (no pain) to 10 (maximal pain).

- **Clinical laboratory parameters**

For each subject, blood samples will be performed at baseline and Day+1 for being analyzed by a central laboratory.

The following parameters will be obtained and assessed:

- Hematology: Red Blood Cells (RBCs), White Blood Cells (WBCs), neutrophils, eosinophils, basophils, lymphocytes and monocytes, platelet count, hemoglobin, hematocrit, Mean red blood Cells Volume (MCV).
- Biochemistry: sodium, potassium, chloride, random glucose, Blood Urea Nitrogen (BUN) / urea, creatinine, eGFR, Cystatin C, total protein, calcium, phosphorus, total bilirubin, unconjugated and conjugated bilirubin, Aspartate Amino Transferase (AST), Alanine Amino Transferase (ALT), alkaline phosphatase, Lactate DeHydrogenase (LDH). Triglycerides (TG).

In female subjects of childbearing potential, a urine or serum pregnancy test will be performed on-site prior to the administration of IMP.

For all other laboratory assessments, the central laboratory will flag laboratory values falling outside of the normal ranges on the central laboratory report (which the investigator should review and sign off) and the investigator will report any values considered clinically significant as an AE or alternatively according to investigator's judgement as medical history if measured at baseline and related to an underlying disease.

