10. SAFETY REPORTING

10.1 Adverse Event

10.1.1 *Definition of Adverse Event*

An Adverse Event (AE) is any untoward medical occurrence in a patient or investigation subject administered a pharmaceutical product and which does not necessarily have to have a causal relationship with this treatment.

An adverse event can therefore be any unfavorable and unintended sign (including an abnormal laboratory finding, for example), symptom, or disease temporally associated with the use of a medicinal product, whether or not considered related to the medicinal product.

Any disease identified and diagnosed by study contrast-enhanced MRI will not be considered as AE.

10.1.2 *Recording/Collection of Adverse Events*

The Investigator or his/her designee will invite the subject to report any abnormality experienced as part of the usual clinical follow-up.

All adverse events, whether considered as related or not to the Investigational Medicinal Product and/or the imaging procedure should be reported in the medical file and the CRF and followed up from onset to resolution or stabilization of sequelae. If no follow-up is performed, the investigator must provide a justification.

In order to ensure complete safety data collection, all adverse events occurring from ICF signature until Day+1, must be reported and followed even if no IMP was administered. The investigator shall document all adverse events in the medical file and the appropriate section of the CRF.

In addition, if occurring after the safety visit at Day+1, events that the investigator thinks may be associated with the study medication/procedure must be reported to the sponsor at the optional Visit 4 and further regardless of the time between the event and the end of the study.

Safety information to be collected by the investigator with the same procedure as adverse events: medication errors and uses outside what is foreseen in the protocol, including misuse and abuse of the product, suspicion of transmission of an infectious agent via an IMP, unusual failure in efficacy, overdose (symptomatic or not), all reports of pregnant or breastfeeding women exposure even if uneventful, all reports of suspected drug-drug interaction with another product (symptomatic or not).

In this protocol, the overdose is defined as more than 0.3 mmol/kg for P03277. Any overdose, with or without adverse event, will be reported as AE and, in addition, on SAE form if the associated event is serious.

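### Section 12.4 pools full adverse event collection to Day +1 with related-only collection afterwards in one any-TEAE percentage, and its three periods are not exhaustive

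*Protocol*

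**What the plan says.** On collection, Protocol section 10.1.2 requires that "all adverse events occurring from ICF signature until Day+1, must be reported and followed even if no IMP was administered". After that the rule narrows. Section 7.2.2 says: "After, AEs that the investigator considers related to P03277 and/or study procedures will be recorded at optional V4". There is no closing date for these late reports: section 10.1.2 wants them "at the optional Visit 4 and further regardless of the time between the event and the end of the study", and section 10.2.2 repeats the duty for events, serious or not, that arise after the subject's follow-up has ended. Visit 4 is optional. Section 9.1.4 places it between 3 days and 13 weeks after dosing, and accepts histology from the two months before dosing instead.

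On analysis, section 12.4 says: "Adverse events occurring after D+1 that the investigators considers as related to P03277 /study procedures will be included in this analysis". It continues: "The time period for the assessment of AEs will be divided into 3 mutually exclusive and exhaustive periods". The first period lies before dosing, the second runs from dosing to the Day +1 visit, and the third is "after safety follow-up until biopsy if it is done". An event is treatment-emergent if it began or worsened after dosing, with no upper time limit. The overview gives the number and percentage of subjects with any TEAE and, in a separate row, with an adverse reaction, meaning an event related to study treatment. Repeats of one preferred term in one subject count once per period. Results are shown by dose and overall on the safety set.

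**The concern.** A percentage of subjects with any TEAE is readable when one collection rule applies over one window. Here about one day of complete collection is joined to a much longer stretch in which unrelated events are left out by design. The resulting figure is neither the one-day TEAE rate nor the rate over the longer follow-up. It is shown by dose, with cohorts of 30 and 10, where one subject is visible in the percentage.

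The second problem is one of definition. The periods are declared to cover everything, and the counting rule is built on them. If a reportable, analysable event can lie outside all three, the rule gives no answer for it.

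**Working it through.** The protocol states no adverse event rate, no expected share of subjects attending Visit 4 and no target figure, so there is nothing to reproduce. The check sets the collection rules (sections 7.2.2, 10.1.2, 10.2.2) against the analysis rules (section 12.4).

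**Step 1. Collection against period.**

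| Window | Collected | Period in 12.4 | Enters the any-TEAE row |
|---|---|---|---|
| Consent to dosing | all events | first | only if worse after dosing |
| Dosing to Day +1 visit | all events | second | yes, related or not |
| After Day +1, up to a biopsy | related only | third | yes |
| After Day +1, no biopsy done | related only | none | yes |
| After the biopsy | related only | none | yes |

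The any-TEAE row therefore draws on two collection rules, and the last two lines of the table have no period. The second line cannot absorb them, because the second period stops at the Day +1 visit.

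**Step 2. Which summaries mix the rules.** Those counting any TEAE do: the overview row, the summary by system organ class and the distribution of event counts. The adverse-reaction row does not. An event related to P03277 is reportable both before and after Day +1, so that row follows one rule throughout.

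**Step 3. The counting rule.** Take a subject without a post-dose biopsy who has an event by Day +1 and a later related event with the same preferred term. If the late event is placed in the second period, the two count as 1. If the third period is stretched to hold it, they count as 2. The subject then moves between two columns of the distribution table and the total differs by 1. The text does not choose. The data review meeting in section 12.4 deals with events that cannot be allocated reliably, in the context of partial dates. A fully dated event outside every period is not that case. This ambiguity does not alter the any-TEAE percentage, where a subject counts once.

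**Step 4. Size of one late event.** Inputs: planned cohorts of 30 and 10, 40 in total (section 8). If k subjects with no TEAE by Day +1 have a late related event, the any-TEAE percentage rises by 100 × k / n points.

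- First cohort: 100 × 1 / 30 = 3.3 points.
- Second cohort: 100 × 1 / 10 = 10 points.
- Overall: 100 × 1 / 40 = 2.5 points.
- With k = 0 the pooled row equals the Day +1 row in every column.

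A subject who already had a TEAE by Day +1 adds nothing to this row.

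**The case against.** The strongest defence has four parts. First, collecting only related events after Day +1 is an open and deliberate choice, and section 12.4 says plainly that they are included. Second, the boundary between the second and third periods falls where the collection rule changes, so a table by period would separate the two. Section 12 describes itself as a summary of a fuller statistical analysis plan, which is not available here and may contain such a table. Third, this is a 40-subject descriptive study without tests. Fourth, nothing happens unless late related events occur.

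Much of this stands. The collection choice is not a fault, the missing table layout is not a finding, and the effect is conditional. What remains is in the protocol's own text: an overview row defined without an end date or split, and a claim of exhaustiveness that the reporting rules contradict.

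Three stronger readings are tempting, and the documents do not support them.

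- A reader might infer that the share of TEAEs judged related is inflated. The protocol plans no such ratio, and its direction would not be fixed. Late events related only to a procedure are TEAEs but not adverse reactions. Assume 6 subjects with a TEAE by Day +1, 3 of them with an adverse reaction: 3/6 = 50.0%. Two new subjects with late P03277-related events give 5/8 = 62.5%. Two with late procedure-only events give 3/8 = 37.5%. These counts are assumed, not taken from the protocol.
- A reader might infer that subjects without a biopsy drop out of the safety analysis. They remain in the safety set (section 12.1) and in the first two periods. Only a late event of theirs lacks a period.
- A reader might infer that late events come only from Visit 4 attenders. Sections 10.1.2 and 10.2.2 require reports beyond that visit. Attendance may affect how actively events are sought, but the protocol gives no figure for this.

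**Conclusion.** The point holds in limited form. The any-TEAE summaries in section 12.4 have no single collection rule, and the three periods are not exhaustive under the protocol's own reporting duties, which leaves the per-period count undefined for some reportable events. The step sizes in the working assume that the safety set equals the planned cohorts; dosed subjects who are later replaced would enlarge the denominators and shrink the steps slightly. No expected total shift can be given, since neither a late event rate nor a Visit 4 share is stated, and the shift may be zero. The adverse-reaction row is sound as planned. The change is worth making because safety is a stated secondary objective, the by-dose columns are small, and the correction loses no data.

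**What to change.** In section 12.4:

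1. Present the any-TEAE, system organ class and event-distribution summaries for injection through the Day +1 visit, with all dosed subjects as denominator.
2. Show later related events in a separate table by dose, split into P03277-related and procedure-related, with the number of subjects who attended Visit 4.
3. Keep all P03277-related events, early and late, in the adverse-reaction row. Cutting that row at Day +1 would remove genuine late reactions from the main safety table.
4. Redefine the third period, for every subject, as running from after the Day +1 visit to last contact or last report, whether or not a biopsy is done. The three periods then cover all reportable events and the counting rule works as written.

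The cost is a few sentences in section 12.4 and one more table. No additional data collection is needed.

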12.5 Handling of Missing Data

No imputation or replacement of missing data will be carried out.

12.6 Interim Analysis

Not applicable

 CONFIDENTIAL	Protocol No. GDX-44-008 Version No.4.0 including amendments 1 and 2 12 December 2017	Page 54 / 64
--	--	--------------

13. STUDY COMMITTEES(S)

The IMP used, in this study, as contrast agent belongs to a well-known product class (GBCA) and there is, a priori, no particular expected safety concerns. In addition, the P03277 has a linear pharmacokinetic profile similar to the other Gd chelates and the preliminary results obtained during the phase I study with several doses of P03277 showed no clinical and biological alert signal.

For all these reasons, an IDMC (Independent Data Monitoring Committee) has not been established for the study.

However, the safety data will be monitored during the study conduct.

14. ETHICAL AND REGULATORY CONSIDERATIONS

14.1 References

The study will be conducted in accordance with the following regulatory / guidance texts:

- World Medical Association Declaration of Helsinki, Ethical Principles for Medical Research Involving Human Subjects, June 1964, and amended in: October 1975 (Tokyo), October 1983 (Venice), September 1989 (Hong Kong), October 1996 (Somerset West), Scotland, October 2000 (Edinburgh), 2002 (Washington), 2004 (Tokyo), October 2008 (Seoul), October 2013 (Fortaleza)
- International Conference on Harmonisation (ICH) of Technical Requirements for Registration of Pharmaceuticals for Human Use: Guideline for Good Clinical Practice E6 (R1) Current Step 4 version dated 10 June 1996
- International Conference on Harmonisation (ICH) of Technical Requirements for Registration of Pharmaceuticals for Human Use: ICH E5 Ethnic Factors in the Acceptability of Foreign Clinical Data
- International Conference on Harmonisation (ICH) of Technical Requirements for Registration of Pharmaceuticals for Human Use: Clinical Safety Data Management: Definitions and Standards for Expedited Reporting E2A Current Step 4 version dated 27 October 1994
- International Conference on Harmonisation (ICH) of Technical Requirements for Registration of Pharmaceuticals for Human Use: General Considerations for Clinical Trials E8 Current Step 4 version dated 17 July 1997
- Directive 2001/20/EC of the European Parliament and of the Council of 4 April 2001 on the approximation of the laws, regulations and administrative provisions of the Member States relating to the implementation of good clinical practice in the conduct of clinical trials on medicinal products for human use
- Commission Directive 2003/94/EC of 8 October 2003 laying down the principles and guidelines of good manufacturing practice in respect of medicinal products for human use and investigational medicinal products for human use
- Commission Directive 2005/28/EC of 8 April 2005 laying down principles and detailed guidelines for good clinical practice as regards investigational medicinal products for human use, as well as the requirements for authorisation of the manufacturing or importation of such products
- EudraLex, The Rules Governing Medicinal Products in the European Union, Volume 4, EU Guidelines to Good Manufacturing Practice - Medicinal Products for Human and Veterinary Use, Annex 13 Investigational Medicinal Products

 CONFIDENTIAL	Protocol No. GDX-44-008 Version No.4.0 including amendments 1 and 2 12 December 2017	Page 55 / 64
--	--	--------------

- US Food and Drug Administration, Title 21 Code of Federal Regulations Part 11 on Electronic Records; Electronic Signatures
- French regulation :
 - o Current version of the French Public Health Code
 - o Decree 2016-1537 dated 16 November 2016 related to research involving human subjects
 - o Loi n° 2004-806 du 9 août 2004 relative à la politique de santé publique
 - o Loi n° 2002-303 du 4 mars 2002 relative aux « Droits des malades et la qualité du système de santé »
 - o Loi n° 2004-801 du 6 août 2004 relative à la protection des personnes physiques à l'égard des traitements de données à caractère personnel et modifiant la loi n° 78-17 du 6 janvier 1978 relative à l'informatique, aux fichiers et aux libertés et la Loi n° 94-548 (1 juillet 1994) relative au traitement de données nominatives ayant pour fin la recherche dans le domaine de la santé. - Décret d'application n° 2005-1309 du 20 octobre 2005.
 - o Méthodologie de référence pour les traitements de données personnelles opérées dans le cadre des recherches biomédicales (MR001), octobre 2010 modifiée 21 juillet 2016.
 - o Bonnes Pratiques de Fabrication, Journal officiel de la République française du 7 janvier 2014, texte n°2 sur 82)

14.2 Institutional Review Board/Independent Ethics Committee and Regulatory/Competent Authorities

As per international regulation, the clinical study may be initiated only after having received the approval by and Institutional Review Board/Independent Ethics Committee (IRB/IEC) and the authorization by the national Regulatory/Competent Authority. The final written approval and authorization must be available for a given investigational site when initiating the study conduct at this particular site. Amongst all documents required locally, the approval and authorization must be obtained for the protocol, investigator's brochure, the subject informed consent form and any other written information or document to be provided to the subjects.

In case of modifications to the study protocol, subject informed consent form or any other written information provided to the subjects, or to any study procedure; the modified documents will be submitted to IRB/IEC and Regulatory/Competent Authority opinions. Modifications may be implemented when the final approval and authorization are available.

In case of an emergency situation when the subjects' safety may be at risk, Guerbet may implement emergency safety measures prior to obtaining IRB/IEC approval and Regulatory/Competent Authority opinion. In parallel to implementing these measures, Guerbet will immediately notify the concerned IRB/IEC and Regulatory/Competent Authorities of such implementation.

The documentation related to the approvals and authorizations must be filed in the Study Master File at Guerbet and at the investigational sites in their respective Investigational Site File.

Notifications of Serious Adverse Events/Reactions to IRB/IEC and Regulatory/Competent Authority will be made according to the national requirements. Safety reporting is described in [Section 10](#) of the present protocol.

 CONFIDENTIAL	Protocol No. GDX-44-008 Version No.4.0 including amendments 1 and 2 12 December 2017	Page 56 / 64
--	--	--------------

